Projected effect sizes and statistical power. To estimate effect size for the primary outcome variables of systolic and diastolic blood pressures, we bracketed over several scenarios with varying pre- to post-intervention differences (i.e., with the fall in pressure following heat therapy being 4.0, 4.5, or 5.0 mmHg greater than following exercise training), and using a SD of 4.5 mmHg from our pilot work and published studies using similar interventions and approaches, which resulted in minimum hypothesized effect sizes of 0.89, 1.00, and 1.11 for Aim 1. Effect sizes for blood pressures were the lowest of our outcome variables; thus, powering for blood pressure will allow adequate power for numerous measurements giving us a global picture cardiovascular and autonomic health. Our prospective power estimates based on a simpler model (two-sample RCT design, modeled as a two-sample t-test), to detect a minimum hypothesized effect size of 0.89 (which is smallest effect size of interest across outcome variables; power 90%; $\alpha=0.05$), indicate the need to enroll 50 subjects (50:50 ratio of study groups; sample size assumes 20% dropout for the per-protocol analysis). Of those preliminarily screened who appear to be eligible, we will consent and enroll up to 250 individuals for further screening for eligibility anticipating only 50 individuals will be eligible for participation in the study. We need 50 study participants to account for rate of attrition once participants are enrolled in the formal study to ensure completion of 40 participant needed for statistical purposes.

D. Research Population, Recruitment Methods, and Compensation

Protocol 1:

The trial will be conducted in a cohort of 50 physically inactive to moderately active men and women with high blood pressure (Elevated, Stage 1, and Stage 2, based on current guidelines)⁴ from the local Eugene and Springfield, OR communities. We will attempt to recruit subjects that represent the ethnicity of Eugene, Oregon and the University of Oregon.

Subjects will be recruited locally (newspaper advertisements, flyers, radio advertisements, in-person recruitment events, online posts, as well as Craigslist and other online advertisements including ad campaigns designed and hosted by marketing companies), as well as referred to us by local physicians and clinics.

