subject is having blood drawn as part of a medical exam, they will be asked to inform their medical provider that they provided blood about equal to that of a standard donation. The magnitude of severity for risks of infection or syncope from the blood sampling is very low, and the probability of these risks occurring is very low. Bruising is temporary and does not pose any long-term risks to the subject, aside from mild discomfort. Pressure will be applied to the site after removal of the needle to assure that any bleeding ceases quickly. A band-aid and/or small gauze pressure wrapping will be applied to the subject's arm to keep the site protected. The risk of infection at the site is low. The subject will be instructed on how to keep the site clean during the days following the study. The probability of the adverse reactions discussed above is low, and the severity is low.

Subject Rights and Withdrawal. Taking part in this research is a voluntary decision made by the research subject. The subjects can stop at any time and their decision whether or not to participate will not affect their relationship with the University of Oregon. By partaking in this research, subjects do not waive any liability rights for personal injury. The investigators may stop a subject from taking part in this study at any time if it is in their best interest, if the subjects do not follow the study rules (e.g., compliance of less than 70% for heat or exercise sessions, or failure to follow study guidelines despite several reminders), or if the study is stopped. For example, if the investigators determine the study is overly stressful for the subject (as indicated by body language and an extremely elevated heart rate and/or blood pressure) they may stop the subject from participating in the study. Or, if subjects express pain or discomfort beyond what is normally expected, the investigators will stop the subject from participating in the study.

Emergency Procedures. In the unlikely event of a medical emergency, we will follow the "Guidance for Human Physiology Investigators on Emergency and Non-Emergency Procedures for Human Subject Research," approved previously by the IRB. In addition, we would provide responding emergency healthcare providers with the MEDICAL HISTORY FORM provided by the subject.

As this human subject research meets the definition of Clinical Trial, we have attached our DATA AND SAFETY MONITORING PLAN.

Protocol 2:

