## 6 Sample Size

**Projected effect sizes.** To estimate effect size for the primary outcome variables of systolic and diastolic blood pressures, we bracketed over several scenarios with varying pre- to post-intervention differences (i.e., with the fall in pressure following heat therapy being 4.0, 4.5, or 5.0 mmHg greater than following exercise training), and using a SD of 4.5 mmHg from our pilot work and published studies using similar interventions and approaches, which resulted in minimum hypothesized effect sizes of 0.89, 1.00, and 1.11 for Aim 1. For MSNA, we used a pre-intervention mean value of 39 $\pm$ 7 bursts/100beats based on our pilot data with 4 HTN subjects, and determined that a post-intervention mean value of 29 $\pm$ 7 b/100bts would represent a clinically significant change (of 10 b/100bts). Thus, for MSNA,  $d = 1.43$ .

Similarly, from our pilot work and our published studies using similar interventions and approaches, calculated effect sizes for  $\beta$ -stiffness  $d = 1.43$ , DAC  $d = 1.70$ , sympathetic baroreflex  $d = 1.33$ , FMD  $d = 2.55$ , carotid wall thickness  $d = 3.33$ , for Aim 2. Effect sizes for blood pressures were the lowest of our outcome variables; thus, powering for blood pressure will allow adequate power for numerous measurements giving us a global picture cardiovascular and autonomic health.

**Statistical power.** Our prospective power estimates based on a simpler model (two-sample RCT design, modeled as a two-sample t-test), to detect a minimum hypothesized effect size of 0.89 (which is smallest effect size of interest across outcome variables; power 90%;  $\alpha=0.05$ ), indicate the need to enroll 50 subjects (50:50 ratio of study groups; sample size assumes 20% dropout for the per-protocol analysis).

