### 7.2 Analysis Populations

Intention-to-Treat will be the primary analysis approach. However, as one goal is to compare outcomes when subjects maintain compliance with heat therapy and exercise training, we will also employ per-protocol analysis as a secondary approach, including subjects with  $\geq 90\%$  compliance. As an exploratory step, we will conduct analyses of variance to compare characteristics of dropouts vs. completers, as this may inform future endeavors.

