#### 7.2.2 Per Protocol Population

- *All subjects who adhere to the major criteria in the protocol with a  $\geq 90\%$  compliance*
- *If  $\geq 90\%$  of participants have full compliance, this analysis will not be performed*

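### The only stated power, 90%, is attached to the secondary per-protocol analysis; none is given for the primary intention-to-treat analysis, and the plan's own inputs give about 78% to 87%

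*SAP*

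**What the plan says.** **Sizing.** SAP section 6, and the matching paragraph on effect sizes and power in section C of the protocol, bracket the treatment difference "with the fall in pressure following heat therapy being 4.0, 4.5, or 5.0 mmHg greater than following exercise training", "using a SD of 4.5 mmHg from our pilot work" and published studies. They then size the trial on a two-sample t-test "to detect a minimum hypothesized effect size of 0.89", with 90% power, alpha 0.05 and 1:1 allocation. The result is 50 to enrol, where the "sample size assumes 20% dropout for the per-protocol analysis". The protocol adds that 50 are needed to "ensure completion of 40 participant needed for statistical purposes".

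**Analysis populations.** SAP section 7.2 says "Intention-to-Treat will be the primary analysis approach", with per-protocol secondary. Section 7.2.1 defines the primary set as a modified intention-to-treat set: any intervention received and at least one post-baseline assessment. Section 7.2.2 defines the per-protocol set as "All subjects who adhere to the major criteria in the protocol with a" compliance of at least 90%, and cancels that analysis if at least 90% of participants are fully compliant.

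**Stopping for poor attendance.** Section G of the protocol gives "compliance of less than 70% for heat or exercise sessions" as one example of a reason for which investigators may stop a participant.

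Neither document gives power for the intention-to-treat set, or the share of participants expected to reach 90% compliance.

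**The concern.** A reader will take the 90% as the power of the primary test. The plan ties it instead to a secondary analysis that may not be run at all. That leaves two questions: what power the same inputs give for the primary set, and whether 90% is right even for the per-protocol set.

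There is also a definitional gap. The protocol counts 40 who complete, whereas the per-protocol set counts those with at least 90% of sessions. The documents do not define these as the same people.

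The stake is interpretation. If the primary test has a one-in-five chance of missing the assumed difference rather than one in ten, a non-significant result is weaker evidence against heat therapy than the stated power implies.

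**Working it through.** **Inputs.** All come from SAP section 6 and section C of the protocol: difference 4.0 mmHg, SD 4.5 mmHg, d = 4.0/4.5 = 0.89, alpha 0.05, target power 90%, 1:1 allocation, 50 enrolled, 20% dropout, so 50 × 0.8 = 40 remaining. Sidedness is not stated in the sizing text. I take the test as two-sided because SAP section 9 tests a null of zero interaction.

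**Step 1: reproduce the stated size.** Normal approximation, n per arm = 2(z₁₋α/₂ + z_power)²/d².

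- For 90%: 2(1.960 + 1.282)²/0.89² = 26.5, so 27 per arm. The t-test needs 28 per arm, 56 analysed, and 56/0.8 = 70 enrolled. The stated 50 is not reproduced.
- For 80%: 2(1.960 + 0.842)²/0.89² = 19.8, so 20 per arm, 40 analysed, and 40/0.8 = 50 enrolled. This matches the plan's 40 and 50 exactly.

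The planned numbers therefore fit 80% power at d = 0.89, not 90%.

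**Step 2: power at the planned numbers.** Noncentral t with df = 2n − 2 and noncentrality λ = d√(n/2), n per arm.

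| Analysed | n per arm | λ | Critical t | Power |
|---|---|---|---|---|
| 40 | 20 | 2.814 | 2.024 | 78.3% |
| 45 | 22.5 | 2.985 | 2.017 | 83.1% |
| 50 | 25 | 3.147 | 2.011 | 86.9% |

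If 20% is the loss before final assessment, the modified intention-to-treat set holds between 40 and 50, because someone who stops after the interim test stays in. Its power with an undiluted 4.0 mmHg is thus about 78% to 87%.

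**Step 3: sensitivity to early stopping (assumption).** Suppose 20% of the heat arm stop after the interim test and get half the added fall, 2.0 mmHg, and all 50 are analysed.

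- Mean difference: 0.8 × 4.0 + 0.2 × 2.0 = 3.6 mmHg.
- Extra heat-arm variance from the mixture: 0.8 × 0.2 × (4.0 − 2.0)² = 0.64.
- Pooled SD: √[(20.25 + 0.64 + 20.25)/2] = 4.535.
- d = 3.6/4.535 = 0.794; at 25 per arm λ = 2.807 and power is 78.5%.

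That is almost the same as 40 analysed with no dilution. The larger number offsets the smaller effect.

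**Step 4: per-protocol set.** At least 90% compliance means 0.9 × 30 = 27 sessions. If all 40 completers reach it, power is 78.3%. If 36 do (90% of completers, an assumed share), n is 18 per arm, λ = 2.670 and power is 73.7%.

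**The case against.** Several points on the other side have force.

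- **Forty may be the per-protocol set.** SAP section 6 can be read as 20% lost between enrolment and the per-protocol set. Section C of the protocol also schedules all 30 sessions before the post-tests, so a completer on schedule exceeds 90%. The 70% figure is only an example of when a participant may be stopped and does not define completion. This stands. A reader might infer that the power statement describes no analysis population at all; the documents do not support that. What remains is that they never say the two groups coincide.
- **The mismatch may cost the primary analysis nothing.** A reader might infer that the intention-to-treat test must have less power because it keeps people who stop early. For example, 20% of the heat arm with no added fall gives 3.2 mmHg and about 67% at 25 per arm. The documents do not support this as a headline. The first scheduled outcome assessment follows 15 sessions, so anyone who stops before it is outside the modified set and dilutes nothing, and anyone who stops after it has had half the sessions. The plan does not say that 4.0 mmHg presumes adherence. The comparator is also active, and the protocol's background says most people comply poorly with exercise, so non-adherence could widen the difference. This stands too.
- **The test might be meant as one-sided**, since the hypothesis is directional. Power would then be 86.8% at 40 and 92.7% at 50. Neither document says so, and the null of zero interaction points to a two-sided test. Even one-sided, 40 analysed falls short of 90%.
- **The planned model is not a t-test.** The repeated-measures mixed model could have different power, but no within-subject correlation is given. The t-test is the plan's own sizing model.
- **The study is described as hypothesis-generating** (SAP section 7.5). That softens the consequence but does not make the stated power correct.

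**Conclusion.** The point holds in a limited form. The only power statement is attached to the secondary analysis, the primary analysis has none, and on a two-sided reading the stated inputs give 90% for neither set. Power is about 78% for 40 analysed and 87% if all 50 are analysed. The shortfall is therefore 3 to 12 percentage points, and it comes from the arithmetic, not from the choice of population.

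The result rests on a two-sided test, the plan's d of 0.89 and its t-test simplification. The dilution figure (about 79%) and the 36-completer figure (74%) depend on shares that the documents do not give, and serve only as sensitivity values.

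**What to change.** In SAP section 6 and the power paragraph of section C of the protocol:

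1. Replace the 90% statement with power for the primary intention-to-treat set, naming the set and the sidedness: about 78% to 87% for 40 to 50 analysed, with an undiluted 4.0 mmHg difference.
2. Add one sensitivity figure, labelled as an assumption, for participants who stop after the interim test. For example, 20% of the heat arm with half the added fall gives 3.6 mmHg and about 79% at 25 per arm.
3. Give per-protocol power separately, at the number expected to attend at least 27 of 30 sessions: 78% if all 40 completers qualify, 74% if 36 do. Say whether the 40 completers are meant to be that set.

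The SAP already records findings made during analysis, so this should be a dated correction using the prospective inputs, not observed results. It needs no extra participants and no change to the analysis; the stated power becomes less favourable.

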## 7 General Analysis Considerations

### 7.1 Timing of Analyses

The final data analysis will be performed by an externally contracted biostatistician after study visits have been completed for all enrolled subjects.

### 7.2 Analysis Populations

Intention-to-Treat will be the primary analysis approach. However, as one goal is to compare outcomes when subjects maintain compliance with heat therapy and exercise training, we will also employ per-protocol analysis as a secondary approach, including subjects with  $\geq 90\%$  compliance. As an exploratory step, we will conduct analyses of variance to compare characteristics of dropouts vs. completers, as this may inform future endeavors.

#### 7.2.1 Intention to Treat or Modified Intention to Treat

- *All participants who received any intervention and who participated in at least one post-baseline assessment*

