**Specific Aim 1:** These studies in mid-life adults will determine if heat therapy can be used to improve cognitive aging and dementia risk, with potentially important clinical implications for the prevention of ADRD. Demonstrating that heat therapy can be used as a novel treatment for essential hypertension is timely and important as there is a clear need for alternatives to exercise training and pharmacological approaches. As HTN is linked to ADRD risk, these studies will allow us to link outcome measures in Protocol 1 (focused on CVD risk) with Protocol 2 (focused on ADRD risk) before and after subjects undergo heat therapy or exercise intervention in Protocol 1. The proposed studies are innovative and include an intention-to-treat randomized clinical trial and detailed high-resolution phenotyping to better understand the improvements in blood pressure regulation following heat therapy. *Overall, this work advances a novel treatment option for those with HTN and in the prevention of CVD and ADRD.*

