**Table 3. Non-derived variables used in study assessments**

Variable	Aim/Primary or Secondary	Description
Protocol 1		
syst_bp_mean	Aim 1/Primary	Continuous; average of 3 systolic BP measurements collected in clinic at pre-, interim-, and post-intervention timepoints
diast_bp_mean	Aim 1/Primary	Clinic diastolic BP; Continuous; average of 3 diastolic BP measurements at 2 screening

		visits collected in clinic at pre-, interim-, and post-intervention timepoints
mean_rest_hr	Aim 1/Secondary	Continuous; average of 3 resting heart rate measurements collected in clinic at pre-, interim-, and post-intervention timepoints
Mean_qc	Aim 1/Secondary	Continuous; average of 3 cardiac output measurements collected in clinic at pre-, interim-, and post-intervention timepoints
Mean_qc	Aim 1/Secondary	Continuous; average of 3 cardiac output measurements collected in clinic at pre-, interim-, and post-intervention timepoints
Protocol 2		
mean_pcalib_gm	Brain biomarkers of ADRD/primary	Continuous; Mean perfusion calibration in gray matter, measure of arterial transit time
mean_pcalib_wm	Brain biomarkers of ADRD/primary	Continuous; Mean perfusion calibration in white matter measured by MRI, measure of arterial transit time

Note: means calculated in REDCap are not considered derived variables for the purposes of this table.

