**HEAT THERAPY VS EXERCISE TRAINING IN HYPERTENSION SAP**

dbp_dipper	Aim 1/Secondary	Categorical; non-dipper <10%, dipper ≥10% to <20%, and extreme dipper ≥20% change in diastolic BP at night calculated from ambulatory BP day and night averages
pwv	Aim 2/Primary	Continuous; average of three pulse wave velocity measurements collected at pre-, interim-, and post-intervention timepoints
il6_lg2	Aim 2/Secondary	Continuous; Biomarker IL-6 with the lower limit of detection (LLD) of 0.031 imputed for <LLD, log2 transformed for normalcy
crp_lg2	Aim 2/Secondary	Continuous; Biomarker CRP with the lower limit of detection (LLD) of 0.031 and upper LD (ULD) of 50 imputed for <LLD and >ULD, log2 transformed for normalcy
et1_lg2	Aim 2/Secondary	Continuous; Biomarker ET-1 with the lower limit of detection (LLD) of 0.031 imputed for <LLD, log2 transformed for normalcy
alb_lg2	Aim 2/Secondary	Continuous; Biomarker urine albumin with the lower limit of detection (LLD) of 0.031 imputed for <LLD, log2 transformed for normalcy
Supine.SBP.low	Aim 3/Primary	Continuous; average of three lowest consecutive supine systolic blood pressure measurements taken every 5 minutes for an hour post-intervention during supine recovery (for Heat Therapy: syst_bp55_ht_s1 to syst_bp110_ht_s1; for Exercise Training: for Heat Therapy: syst_bp55_ex_s1 to syst_bp110_ex_s1)
Supine.DBP.low	Aim 3/Primary	Continuous; average of three lowest consecutive supine systolic blood pressure measurements taken every 5 minutes for an hour post-intervention during supine recovery (for Heat Therapy: syst_bp55_ht_s1 to syst_bp110_ht_s1; for Exercise Training: for Heat Therapy: diast_bp55_ex_s1 to diast_bp110_ex_s1)
Supine.SBP.1.ch	Aim 3/Primary	Change from average pre-session resting SBP to Supine.SBP.low
Supine.DBP.1.ch	Aim 3/Primary	Change from average pre-session resting DBP to Supine.SBP.low
eGFR	Aim 1/Exploratory	eGFR was calculated using the CKD-EPI Creatinine-Cystatin Equation (2021) using the CKDEpi_RF.creat.cys function in the nephron R package and rounded to two decimal places
uacr	Aim 1/Exploratory	Urine albumin creatinine ratio (mg/g) was calculated by dividing urine albumin by urine creatinine/1000 rounded to 2 decimal places
Protocol 2		
cognitive_score	cognitive/Primary	Averaged z-scores (centered & divided by standard deviation) of age-corrected picture sequence score (age_cor_score)

		and age-corrected list-sorting score (list_age_cor_scpre)
--	--	--

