#### 7.4 Missing Data

Descriptive statistics will be computed to understand the nature of the data collected, and to identify outliers and missingness patterns. We will follow procedures to minimize biases and limit power loss as a result of attrition, such as the use of mixed effect models that allow for missing data, and employ multiple data-imputation methods if greater than 10% of a predictor or covariate of interest is missing. Proposed analyses are designed to limit biases even when assumptions of data missing completely or missing at random do not hold. Participants with any study visits post-intervention will be included in analyses.

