## 9 Efficacy Analyses

For primary analyses for Protocol 1 Aims 1, primary outcomes will be compared between groups (heat therapy vs exercise training) over time (within subject repeated measurements) using two-way repeated measures mixed model including an interaction between intervention group and timepoint with pre-defined contrasts. For Specific Aim 1, to test the hypothesis that heat therapy improves blood pressure (both in clinic and 24H ambulatory) better than dynamic aerobic exercise, the null hypothesis will be that the interaction between group and timepoint is equal to 0. For Aim 2, to determine whether heat therapy will improve biomarkers of arterial health (arterial stiffness & biomarkers of systemic

inflammation and oxidative stress) and compare responses to exercise training, the null hypothesis will be that the interaction between intervention group and timepoint is equal to 0. For Aims 1 and 2 exploratory analyses, ANCOVA will be performed for primary and secondary outcomes, with pretest values entered as a covariate and treatment condition specified as a fixed factor. Demographic and physiological variables (age, sex, BMI) and pre-intervention blood pressure will be added one at a time to the ANCOVAs to test for an interaction on treatment effects. For Aim 3, we will use ANCOVA models to determine the predictive potential of acute post-exercise hypotension response for chronic changes in blood pressure, with pretest values entered as a covariate and systolic and diastolic blood pressure specified as a fixed factor. Analyses will be performed on the Intention to Treat population. Additionally, change from pre- to post-intervention in ambulatory and in clinic systolic and diastolic pressure will be correlated with change from pre- to post first intervention session supine systolic and diastolic blood pressure by Pearson correlation.

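### The primary set labelled intention-to-treat is a modified ITT set: SAP 7.2.1 requires treatment and a post-baseline assessment, and SAP 7.4 words inclusion differently

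*SAP*

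**What the plan says.** SAP 7.2 states that "Intention-to-Treat will be the primary analysis approach". The objectives in 4.1 say the studies "include an intention-to-treat randomized clinical trial", and Section 9 adds that "Analyses will be performed on the Intention to Treat population". Section 8.2 also uses the ITT label when it keeps one ineligible randomised participant in the dataset.

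The only operational definition is in 7.2.1, whose heading offers both ITT and modified ITT: "All participants who received any intervention and who participated in at least one post-baseline assessment".

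SAP 7.4 has its own inclusion sentence: "Participants with any study visits post-intervention will be included in analyses". In Table 3 clinic pressures are "collected in clinic at pre-, interim-, and post-intervention timepoints", so there the term means the last of three timepoints. In Table 4 the same term is used for supine readings "taken every 5 minutes for an hour post-intervention during supine recovery", which is the hour after the first session.

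Section 8.1 identifies everyone randomised through the REDCap variable int, so the full randomised set can be recovered.

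**The concern.** Intention-to-treat protects the comparison because membership is fixed at randomisation. Here it depends on two later events, starting the assigned treatment and attending a test. Participants are not blinded (SAP 5.3), and hot immersion and supervised cycling can put off different people, so both events can depend on the arm.

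The gap is wider than non-starters. The first scheduled efficacy test after baseline follows 15 sessions. A participant could attend several weeks of treatment, leave, and be absent from an analysis labelled ITT. The protocol's section on withdrawal also lets investigators stop a subject, for example for compliance below 70%.

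The 7.4 sentence is a second inclusion statement that is not aligned with 7.2.1. An externally contracted biostatistician does the final analysis (SAP 7.1), so the set should be reproducible from the text alone.

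**Working it through.** **1. Who is in under each rule**, taking the interim test as the first post-baseline assessment (the SAP does not define that term):

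- Randomised, never started: in an all-randomised set; out under 7.2.1.
- Started, left before the interim test: in an all-randomised set; out under 7.2.1. At 3 to 4 sessions a week, 15 sessions take 15/4 = 3.75 to 15/3 = 5 weeks.
- Interim test only: in under 7.2.1; unclear under 7.4.
- Final test done: in under every rule.

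The Section 9 model crosses intervention group with timepoint on repeated measurements. If pre-intervention pressure is one of those measurements, baseline-only participants can enter the model, and 7.2.1 is what keeps them out.

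**2. Inputs for size.** The SAP gives 50 participants at 1:1 (25 per arm), a target difference of 4.0 mmHg, SD 4.5 mmHg and 20% dropout. The effect size reproduces: 4.0/4.5 = 0.89. The dropout is 0.20 × 50 = 10 people. Assume, for illustration, that half of them (5) leave before the interim test and that all five are in the heat arm.

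**3. Early dropout that depends on observed baseline pressure.** Assume residual variance 10, so the SD of a change is √(2 × 10) = 4.47, close to the SAP's 4.5 if that is an SD of change. Between-person variance is not given; take 40 to 80. Let the five highest baselines in the heat arm leave.

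- The mean of the highest 5 of 25 standard normal values is 1.345 (numerical integration).
- The remaining 20 therefore have a mean baseline lower by (5/20) × 1.345 = 0.336 SD, where SD = √(between + 10).
- The share of that shift which is measurement noise, absent at follow-up, is 10/(between + 10).
- Bias if the five are dropped = 0.336 × 10/√(between + 10).
- Between = 40: 3.36/√50 = 0.48 mmHg. Between = 80: 3.36/√90 = 0.35 mmHg.

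The true difference is −4.0. With the five dropped, the expected estimate is about −3.5 (−4.0 + 0.48) to −3.65 (−4.0 + 0.35). A simulation of a random-intercept model with these variances (2,000 runs each, simulation error about 0.03) gave −3.49 and −3.61 with them dropped, and −3.97 in both cases with their baselines kept. When the five left at random, the two analyses agreed to within 0.01.

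**4. Early dropout that depends on the unseen response.** Suppose k of 25 heat participants leave early and would have had no extra benefit. The all-randomised difference is 4.0 × (25 − k)/25: 3.84 for k = 1 and 3.20 for k = 5. The restricted set overstates it by 0.16 to 0.80 mmHg. Simulating k = 5 gave about −4.0 whether the baselines were kept or dropped, against a true −3.2. The model in effect gives leavers the mean change of their arm, so adding baselines does not help.

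**5. Power.** For the plan's t-test at d = 0.89, two-sided 0.05, power is 86.9% with 25 per arm and 78.3% with 20. The first figure needs 50 observed changes. People without a final test supply none, whichever set is named.

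**The case against.** The plan partly discloses the restriction. The 7.2.1 heading includes modified ITT, a CONSORT diagram is planned (8.1), and 7.2 compares dropouts with completers. Baseline-only participants add little information to a group-by-time contrast, and the documents do not show that anyone was excluded by the rule. All of this is true. It lowers the stakes, but it does not supply an all-randomised estimate. Sections 7.2, 8.2 and 9 use the ITT label without qualification, and a flow diagram shows counts, not effects.

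Three stronger readings are tempting and should be resisted.

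- *That 7.4 drops interim-only participants.* It is an inclusion sentence: it contains no word such as only and states no exclusion. Its key term has two senses in the SAP. The same section relies on mixed models that tolerate missing values, 9.1 models interim pressure as an outcome, and 7.2.1 keeps these people. It is loose wording that conflicts on one reading; it does not establish a completer analysis.
- *That the set definition costs power, 87% down to 78%.* That difference comes from missing final tests and would remain after the fix.
- *That the fix would remove a 0.8 mmHg bias.* That figure assumes five leavers from one arm with no benefit, which nothing in the documents supports. Step 4 shows that the fix would leave it untouched.

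**Conclusion.** The point holds as a mislabelled primary population together with an unaligned inclusion sentence. The set called ITT is conditioned on post-randomisation events in a trial where participants know their arm, and no all-randomised set is defined.

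The demonstrable gain from correcting it is modest. It gives a true label, one reproducible set, and protection when early dropout depends on observed baseline pressure. That protection is worth about 0.4 to 0.5 mmHg, roughly a tenth of the 4.0 mmHg target, in a scenario that rests on assumed variances and on all five leavers being the highest baselines in one arm. The shift would reverse if they came from the exercise arm, would tend to cancel if both arms lost similar people, and would be nil if dropout were random.

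A reader might infer that the primary result is invalid, or that interim data will be discarded. The documents support neither. Not-at-random dropout is a separate matter: 7.4 claims that bias is limited even then, but names no sensitivity analysis for it.

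**What to change.** 1. In 7.2.1, define ITT as all randomised participants, in the arm assigned, identified by the variable int.
2. In Section 9, state that the mixed model uses every available pre, interim and post value with baseline as one of the responses, so baseline-only participants stay in.
3. Label the present set modified ITT and report it as a sensitivity analysis.
4. Report, by arm, how many were randomised, started, reached the interim test and reached the final test, with reasons for exclusion.
5. Reword 7.4 to refer to any post-baseline (interim or post-intervention) assessment, or delete the sentence and refer to 7.2.1.
6. To support the 7.4 claim about data not missing at random, add a separate sensitivity analysis, for example shifting the unobserved outcomes of leavers by arm over a stated range.

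The cost is SAP wording and a short re-run, since the baseline data are already collected. Section 8.2 reports a finding made during analysis, so the change should be entered as a dated amendment. The downside is small: baseline-only participants add little information, and items 1 to 5 neither raise power nor remove not-at-random bias.
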